Using a Stage Model approach (20), the primary aim of this study is to examine the feasibility and acceptability of a resilience intervention for chronic pain among older adults. Intervention modules will specifically engage hope, self-efficacy, positive affect, and pain acceptance as these factors demonstrated the strongest relationships with clinical pain, disability, and psychological functioning from the PI's previous work (NIH K99 Award). Chronic low back pain (cLBP) will be the targeted population given that it represents the most debilitating and therapeutically-challenging pain condition among geriatric populations. We will conduct a pilot study to test the feasibility and acceptability of the intervention in this patient population (primary aim), explore whether the intervention engages the proposed resilience targets (i.e., hope, self-efficacy, positive affect, pain acceptance), and assess whether changes in these factors result in improvements in pain outcomes (i.e., NIH Science of Behavior Change approach (21)). Achievement of these aims will provide a strong framework for future intervention research examining mechanisms that promote adaptive health and pain-related functioning in aging populations.

Specific Aim 1: *Conduct a pilot test to examine feasibility, acceptability, and tolerability of a resilience intervention for older adults with cLBP.* We will assess adherence and retention rates, and evaluate ratings of acceptability through brief assessments and eliciting qualitative feedback from participants at post-intervention. **Hypothesis 1.** Individuals in the resilience intervention will report high adherence to and satisfaction with the intervention.

Specific Aim 2: *Assess whether a resilience intervention facilitates improvements in hope, self-efficacy, positive affect, and pain acceptance and whether changes in these processes result in improved pain-related outcomes.* Intervention modules will be adapted from the existing positive psychology literature and validated self-report measures will be used to verify engagement in the specific resilience targets. **Hypothesis 2.** We hypothesize that a resilience intervention will improve pain severity, pain interference, negative affect, and quality of life by increasing hope, self-efficacy, positive affect, and pain acceptance.

7. Research Plan:

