General Overview of Procedures. All potential participants will undergo an initial phone screening interview, via telephone or in person. The initial screening will include questions regarding pain, age, and additional health history information to ensure that no exclusion criteria are present. Those who meet study inclusion criteria will also be screened for COVID-19 using the COVID-19 phone screening form. If still eligible, participants will be scheduled for an individual baseline assessment during which informed consent will be reviewed, medical and demographic history will be obtained to ensure eligibility, questionnaires will be administered, and a physical performance battery will be conducted to examine lower extremity function. At the completion of the baseline assessment, eligible participants will be scheduled for a 7-week program (90 min/session) in which participants' complete activities designed to enhance hope, positive affect, pain acceptance, and self-efficacy. Participants will complete weekly home activities and will be asked to bring the home assignments into each session. Participants can miss only one session without making it up or up to two sessions if made up with individual sessions in person, over the phone, or using a PHI Zoom call. Given evidence that intervention effects on pain and psychological outcomes in older adults are strongest when delivered using group-based approaches (relative to an individual format) (22), we have chosen to administer our protocol via groups.

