Cognitive Testing. The Montreal Cognitive Assessment (MoCA) (25) is a widely used screening assessment for detecting cognitive impairment. It was validated in the setting of mild cognitive impairment and has subsequently been adopted in numerous other settings clinically. Participants with scores <26 will be excluded from participation as this could interfere with completion of the study intervention. The alternative/Equivalent version of the MoCA (Version 7.2) will be used to decrease possible learning effects when the MoCA (Version 7.1) has been administered within the past 3 months of study participation. This will serve as a safeguard for test-retest effects for participants who may have recently participated in studies requiring the administration of this instrument.

Physical Performance Battery. The Back Performance Scale (BPS) (26) consists of five tests (i.e., sock test, pick-up test, roll-up test, fingertip-to-floor test, lift test) to assess mobility-related activities in individuals with back pain. Each test is scored from 0 to 3, and a total summed score ranging from 0 to 15 is computed (higher scores equal worse functioning).

Sessions 2-8 (Intervention Delivery):

Intervention Procedure. All sessions will be administered by the PI, Co-I, and/or interventionist (masters/PhD level psychologists). Due to COVID-19, intervention sessions (Week 1 – Introduction and Background through Week 7 – Review of Skills and Wrap-Up) may be delivered online through PHI Zoom. To standardize the application of the intervention and ensure treatment fidelity, the resilience intervention is manualized and includes interventionist and client workbooks with materials and handouts for discussion. Client workbooks are written at the 6th grade reading level as measured by Flesh-Kinkaid Grade Level estimates. These intervention workbooks have been reviewed in an earlier phase of this trial (ARIAA 2A), whereby we conducted semi-structured focus groups and key informant interviews with approximately 47 older adults with cLBP to provide feedback on the treatment manual (IRB201802729). Interventionists will be provided with a checklist of procedures specific to each session, and each checklist will be reviewed to ensure treatment adherence. Participants who miss a group visit will be allowed to complete an individual make-up session, with the stipulation that only two missed sessions will be permitted.

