in-session activities, and assignment of homework. The intervention will be comprised of the following activities. **Week 1: Introduction and Background.** Participants will be provided with instruction on group therapy guidelines (e.g., confidentiality, respect, privacy), an overview of the purpose and structure of the program, and rationale for the use of resilience-enhancing activities for the management of cLBP. Participants will also be given education on cLBP etiology and symptoms and provided the opportunity to discuss their own personal experiences associated with chronic pain. As a home exercise, participants will be asked to complete a character strengths survey. **Week 2: Pleasant Activities.** During the second session, participants will be given instruction on how to increase the number of pleasant events in their life and will be provided with a list of pleasant activities to choose from (31). For their home practice, participants will be encouraged to engage in three pleasant activities over the week and to record things they are grateful for. **Week 3: Pain Acceptance.** Participants will receive instruction on valued activity, psychological flexibility, and mindfulness-based exercises for enhancing pain acceptance and awareness. A values assessment will be administered to assist participants in identifying important values in their life (32). **Week 4: Hope and Goal-Setting.** Based on Snyder's theory of hope (27), participants will focus on their personal strengths and learn ways in which to create attainable goals through the development of pathways and agency thinking. Participants will be asked to develop a goal that they would like to achieve over the course of the intervention to facilitate hopeful thinking and goal-directed behavior, and to identify areas in their life that inspire hope (33). **Week 5: Positive Events and Reappraisal.** To increase attentional focus on positive events, participants will be taught ways in which to minimize the impact of adverse events and to downregulate negative emotions and thoughts through positive reappraisal (34). As a home-based activity, participants will be encouraged to record, at minimum, one positive event that occurred every day, as well as negative events in which they had to practice positive reappraisal (35). **Week 6: Pain Self-Efficacy.** While it is anticipated that self-efficacy will gradually be fostered throughout the course of the intervention (i.e., skills mastery experiences, feedback on progress, social persuasion through group support), this session will complement ongoing training by targeting problem-solving skills and confidence building, as well as empowering participants to promote adaptive pain management behaviors. Participants will be asked to engage in diaphragmatic breathing as a form of relaxation and to note areas of accomplishment over the course of the intervention (36, 37). **Week 7: Review of Skills and Wrap-Up:** Skills learned in the previous sessions will be reviewed and specific plans for maintenance of resilience activities will be discussed. Participants will also complete post-treatment outcome questionnaires and provide feedback on the intervention program.

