
3-Month Follow-Up Assessment

Questionnaires will be administered via REDCap approximately 12 weeks after completion of the intervention to be completed online at home. These questionnaires will assess pain intensity and interference, mood, quality of life, and use of intervention materials and skills since the conclusion of the group sessions.

Study Questionnaires:

Several questionnaires will be administered to assess general health, pain-related symptoms, and psychological functioning. In order to distribute participant burden, some of the questionnaires administered during Visit 1 and Visit 8 will be dispensed either during the session or at home between sessions (either via our secure internet-based data collection system [i.e., REDCap] or on paper, depending on the participant's preference).

Measures of Treatment Acceptability. Treatment credibility questions (38) were adapted for the current study as a treatment expectancy measure and will be administered during Visit 1 and Visit 2 consisting of the following items: 1) reasonableness of treatment, 2) willingness to undergo treatment, 3) confidence in recommending the treatment to others, 4) confidence that the treatment will help with pain coping, 5)

IRB Project #: 201901927

IRB Version: 12/16/2021

confidence that the treatment will decrease pain, 6) confidence that the treatment will eliminate pain, and 7) expectation for improvement.

The 8-item Client Satisfaction Questionnaire (CSQ-8) (39) will be administered after the intervention as an assessment of treatment satisfaction. Items are rated on a 4-point Likert scale and measure aspects related to the quality of treatment, willingness to recommend the treatment, and general satisfaction with the treatment.

As a treatment evaluation and to better understand their perceptions of the intervention, participants will be queried at posttreatment on their satisfaction with the intervention components, contentment with the structure of the intervention, and recommendations for intervention improvement. Participants will also be asked to indicate the usefulness of each intervention session module and home activity on a 5-point Likert scale ranging from 0 ("not at all") to 4 ("extremely").

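### Satisfaction and Aim 2 change are collected only at or after Week 7, with no described collection from people who stop attending, so these figures may be too favourable

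*Combined protocol and SAP*

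**What the plan says.** The measures at issue all come at the end of the programme.

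- **Satisfaction** (section 7, Measures of Treatment Acceptability): "The 8-item Client Satisfaction Questionnaire (CSQ-8) (39) will be administered after the intervention as an assessment of treatment satisfaction". The programme evaluation, which includes usefulness ratings for each module and home activity, is also a post-treatment measure.
- **Outcomes and feedback** (section 7, Intervention Content, Week 7): "Participants will also complete post-treatment outcome questionnaires and provide feedback on the intervention program".
- **Specific Aim 1** (section 6): the investigators will "evaluate ratings of acceptability through brief assessments and eliciting qualitative feedback from participants at post-intervention". Hypothesis 1 reads: "Individuals in the resilience intervention will report high adherence to and satisfaction with the intervention".
- **Aim 2 analysis** (section 7, Statistical Methods): paired t-tests, a half-SD rule for clinically significant change, and correlations of residualized change scores. Each needs a post-intervention value. No analysis set or missing-data rule is given.
- **Attrition** (same section): a target of 50, a 20% allowance, 10 added, total 60. Completers and dropouts are to be compared on baseline characteristics.

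Other passages bear on who would be reached. On attendance, the General Overview of Procedures says: "Participants can miss only one session without making it up or up to two sessions if made up with individual sessions"; Intervention Procedure allows make-up sessions "with the stipulation that only two missed sessions will be permitted". On home completion, Study Questionnaires says that, to spread burden, "some of the questionnaires administered during Visit 1 and Visit 8 will be dispensed either during the session or at home between sessions". On later follow-up: "Questionnaires will be administered via REDCap approximately 12 weeks after completion of the intervention to be completed online at home".

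**The concern.** An acceptability pilot particularly needs the views of people who gave up on the programme, and as described they have no route to give a satisfaction rating. Satisfaction is one of two acceptability measures named in Statistical Methods. The other, treatment credibility, is taken at Visits 1 and 2 and so cannot show how people judged the programme as a whole. For Aim 2, leavers have a baseline value but no post value, so they drop out of all three analyses without any stated rule.

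At stake are the satisfaction half of a hypothesis under the primary aim, and the estimates of change that the pilot is meant to pass on to later intervention research. Retention and completion rates would show how many were lost, and the baseline comparison might show who they were. Neither shows what leavers thought or how they changed.

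**Working it through.** **Step 1. The plan's own figure.** 50 × (1 + 0.20) = 60, so the stated total is reproduced. It implies two possible losses: 10 of 60 (60 − 50, or 16.7%) or 12 of 60 (20% of 60). Neither is a count of missing forms. Completion means attending all seven sessions, so someone who misses one or two is a non-completer but can still give Week 7 data. The plan also does not say whether attrition includes people who enrol but never start.

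**Step 2. Formula.** With n responders and m people without a post value:

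mean over all commencers = (n × responder mean + m × leaver mean) / (n + m)

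Hence bias of the responder mean = [m / (n + m)] × (responder mean − leaver mean), which is zero when the two means agree.

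**Step 3. Inputs.** From the plan: 60 and 20%. All else is assumed: responders change by 0.50 SD; 50% of responders meet the half-SD rule; the mean CSQ-8 item score in responders is 3.5, with items scored 1 to 4 (the protocol gives a 4-point scale but not the scoring). Leavers' change is set at 0, 0.50 or 1.00 SD, that is, 0.50 SD worse, the same, or 0.50 SD better. The first two rows treat all 60 as commencers. The plan calls 20% conservative, so 6 of 60 is added, and the last row supposes that 4 of the 12 never start.

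| Missing of commencers | Mean change (SD) if leavers change 0 / 0.50 / 1.00 | Half-SD share, none to all leavers | CSQ-8 item mean if leavers score 1 / 2.5 / 4 |
|---|---|---|---|
| 10 of 60 | 0.42 / 0.50 / 0.58 | 41.7% to 58.3% | 3.08 / 3.33 / 3.58 |
| 12 of 60 | 0.40 / 0.50 / 0.60 | 40% to 60% | 3.00 / 3.30 / 3.60 |
| 6 of 60 | 0.45 / 0.50 / 0.55 | 45% to 55% | 3.25 / 3.40 / 3.55 |
| 8 of 56 | 0.43 / 0.50 / 0.57 | 42.9% to 57.1% | 3.14 / 3.36 / 3.57 |

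Worked entries for 10 missing:
- Change: (50 × 0.50 + 10 × 0) / 60 = 25/60 = 0.42.
- Half-SD share: 25/60 to 35/60.
- CSQ-8: (50 × 3.5 + 10 × 1) / 60 = 185/60 = 3.08, and (50 × 3.5 + 10 × 4) / 60 = 215/60 = 3.58.

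The outer CSQ-8 values are limits, reached only if every leaver gives the lowest or highest score on every item. The table does not cover the correlations, which selective loss could move in either direction.

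**The case against.** The strongest reply is that the point rests on silence. The CSQ-8 and programme evaluation are not expressly limited to attenders, and some Visit 8 forms may be completed at home. A reader might infer that the plan shuts leavers out, or that passing the missed-session limit ends assessment. The documents do not support that: neither attendance passage mentions loss of post-treatment assessment. What stands is that no collection from leavers is described either. Home completion covers some forms, between sessions, and for reasons of burden.

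The 3-month assessment is a partial answer. It is done from home and covers pain, interference, mood and quality of life. It is timed from completion of the intervention, but its description also refers to the end of the group sessions, so it could be read as running on the programme's calendar and reaching leavers. Even so, it lists no satisfaction measure and does not appear in Statistical Methods.

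It is also fair that leavers contribute acceptability data earlier. Credibility at Visits 1 and 2 includes willingness to recommend the treatment. Engagement is rated by therapist and participant at each session attended, and a home-activity questionnaire is given from Visit 3. It would be wrong to conclude that acceptability is measured only in those who finish. These sources inform on leavers in part, but they do not measure overall satisfaction or change.

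Finally, this is a Stage I pilot with descriptive Aim 1 analyses, no satisfaction threshold and no power target. That limits the weight of the point. It does not remove it, because acceptability belongs to the pilot's primary purpose.

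**Conclusion.** The point holds as a gap in data collection with a possible bias. Followed as written, the plan draws the satisfaction part of Hypothesis 1 and all Aim 2 change from people who reach and answer the post-treatment forms. Completion rates, the enrolled-to-commencing ratio, credibility and the per-session ratings are not affected in the same way.

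A reader might infer that the results will be inflated, or that 12 people will lack data. The documents show neither. An over-favourable direction is plausible because dissatisfaction is a natural reason to leave, but that is judgement; people also leave for reasons unrelated to the programme. If leavers changed by 0.50 SD less than responders, the overstatement would be about 0.08 SD (10 of 60) or 0.10 SD (12 of 60). These sizes rest entirely on assumed responder and leaver values.

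This is a worthwhile, inexpensive improvement and not a fatal flaw.

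**What to change.** 1. At the scheduled Week 7 date, invite everyone who commenced treatment and has not withdrawn consent, whatever their attendance, to complete the CSQ-8, the Aim 2 outcomes and the programme evaluation by REDCap or paper, both already in use. Limit the module and home-activity usefulness items to sessions attended, so that nobody rates material they never received.
2. Report the number responding by sessions attended, with all commencers as the denominator.
3. Add simple bounds for missing post values on three summaries: mean CSQ-8 score, mean change, and the share meeting the half-SD rule.

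The cost is protocol wording, a few extra invitations and three short sensitivity rows. The sponsor should also state whether the $60 payment attached to Session 7 applies to forms returned by people who did not attend it. The downside is that response from leavers may be low, and the estimates may be wider or less favourable. Even then, the denominator and bounds would make the uncertainty visible.

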Statistical Methods. The goal of the study will be to target 50 participants for the pilot intervention. Accounting for a conservative 20% attrition rate, we will recruit an additional 10 participants (Total $N=60$). This sample size is feasible and will provide stable estimates of dropout rates, feasibility, and acceptability of the intervention protocol. We anticipate screening an additional 70 participants who may not meet eligibility criteria (i.e., screen failures). **Data Analysis: Specific Aim 1.** The analysis of feasibility, tolerability, and acceptability outcomes will be predominantly conducted with descriptive statistics, with means and standard deviations reported. To assess feasibility, we will calculate a ratio between participants enrolled versus the number of participants commencing treatment. Tolerability will be examined by measuring completion rates (i.e., participants completing all seven sessions of the intervention). Participant acceptability of the intervention will be assessed through treatment credibility ratings and satisfaction with the program (59). Chi-square tests and between-group t -tests will be used to compare group differences in baseline characteristics between completers and participant dropouts. **Specific Aim 2.** To assess change in primary study outcomes (i.e., pain severity, pain interference, negative affect, quality of life), mean differences from pre- to post-intervention will be calculated using paired samples t -tests. Clinical significance of treatment changes will be determined by identifying participants whose raw change score for each outcome variable is greater than one-half of a standard deviation from their baseline score (60, 61). Using residualized change scores (i.e., difference between the post-intervention value with the pre-intervention score covaried out), Pearson correlations will be computed to examine associations between outcome and treatment target change scores.

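### Recruiting 60 at the stated 20% attrition leaves an expected 48 participants, not 50, because the extra 10 is 20% of 50 rather than of 60

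*Combined protocol and SAP*

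**What the plan says.** The sample size is set out in section 7, Research Plan, under Statistical Methods. It begins with the target: "The goal of the study will be to target 50 participants for the pilot intervention". The dropout allowance follows: "Accounting for a conservative 20% attrition rate, we will recruit an additional 10 participants", and the total is given as 60.

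The justification is descriptive: "This sample size is feasible and will provide stable estimates of dropout rates, feasibility, and acceptability of the intervention protocol". No significance level, power, effect size or precision target is given.

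Screen failures are counted apart from these figures: "We anticipate screening an additional 70 participants who may not meet eligibility criteria". No other section gives a different target, attrition rate or total.

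**The concern.** The allowance looks as if it was taken as a percentage of the wrong base. Ten is 20% of the 50 wanted at the end, whereas dropout is a fraction of those who start. If so, the plan's total falls short of its own target at its own attrition rate.

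Little turns on this numerically. It deserves correction because retention is one of the things this feasibility pilot sets out to measure (Specific Aim 1), and the planned retained number is a natural figure to compare with the observed one.

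**Working it through.** **Inputs**, all from Statistical Methods: target 50; attrition 20%; added for attrition 10; total recruited 60. The 70 screen failures are additional and do not enter the sum.

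**Reproducing the plan's figure.** Multiplying the target by one plus the attrition rate gives 50 × 1.20 = 60, which matches exactly.

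**Number retained from 60.**
- Expected lost: 60 × 0.20 = 12.
- Expected retained: 60 × 0.80 = 48, which is 2 below 50 (2/50 = 4%).

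**Number needed to retain 50 at 20% attrition.** Divide the target by the retention rate: 50 / 0.80 = 62.5, rounded up to 63. Check: 62 × 0.80 = 49.6 and 63 × 0.80 = 50.4.

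**Attrition rate at which 60 is enough.** 1 − 50/60 = 10/60 = 16.7%.

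**Sensitivity to the attrition rate.**

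| Attrition | Expected retained from 60 |
|---|---|
| 10% | 54 |
| 15% | 51 |
| 16.7% | 50 |
| 20% | 48 |
| 25% | 45 |

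**Chance of keeping at least 50 at 20% attrition.** If dropouts are independent (an assumption), the number retained is binomial with probability 0.80. The chance of 50 or more is 0.323 from 60 recruits and 0.623 from 63.

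The intervention is delivered in groups ("we have chosen to administer our protocol via groups"), so dropouts may be correlated. As an upper illustration, take groups of 10 and an intraclass correlation of 0.10, neither of which is in the documents. The design effect is 1 + 9 × 0.10 = 1.9, the variance is 60 × 0.8 × 0.2 × 1.9 = 18.24 and the SD is 4.27. The normal approximation gives 1 − Φ((49.5 − 48)/4.27) = 0.363. Correlation hardly changes this chance, and it does not change the expected 48.

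**Effect on Aim 2.** For the paired t-test, with 80% power and two-sided 5% (both assumed), the detectable standardized difference is 0.413 with 48 participants and 0.404 with 50.

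**Retained is not the same as completing.** Specific Aim 1 defines completion as "participants completing all seven sessions of the intervention", while the General Overview of Procedures says "Participants can miss only one session without making it up". Someone can therefore stay in the study within the rules and not count as a completer. The 48 is an expected number retained, and the number completing could be lower.

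**The case against.** The strongest objection is that the plan never says 50 must remain. It says only that 50 are targeted for the pilot intervention, and it gives no base for the 20%. That is true of the wording. However, adding participants to account for attrition only makes sense if 50 is the number meant to be left. Treating the 10 as replacements does not rescue the sum either, since replacements would drop out at the same rate.

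Second, the plan calls the rate conservative, so actual attrition may be lower, and anything up to 16.7% still leaves 50. This also stands as far as it goes. But a conservative rate is chosen so that the target is met even at that rate, and here it is missed.

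Third, nothing depends on 50. There is no power statement, precision target or progression criterion. Uptake, completion and dropout can all be measured on the 60 enrolled, and the Aim 2 figures barely move. This stands in full and is why the point is minor. A later trial would also be expected to use the dropout observed here rather than this planning allowance, so no harm to future planning is claimed.

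**Conclusion.** The error is real and minor. At the stated 20% attrition, 60 recruits leave an expected 48, two fewer than the target; an expected 50 would need 63. The allowance of 10 matches 16.7% attrition. Neither the screen failures nor any other section repairs the sum.

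The conclusion rests on one reading, that 50 is the number intended to remain after attrition. The expected values need no further assumption. The probabilities and detectable differences above are illustrations under assumptions that the plan does not state. No analysis or conclusion of the study is invalidated.

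**What to change.** Keep the total at 60 and correct one sentence in Statistical Methods. Either state that 60 recruits are expected to leave 48 retained at 20% attrition, or state that the allowance of 10 corresponds to 16.7% attrition. Use the word retained rather than completing, given the seven-session definition of completion. The cost is wording only; if the first option is taken, the planned retained number is 48 rather than 50.

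As a recommendation, not a correction of error: the plan says of feasibility that "we will calculate a ratio between participants enrolled versus the number of participants commencing treatment". It would be clearer to report uptake as the proportion commencing among those enrolled, and to give seven-session completion and dropout as proportions too, each with a stated denominator and a 95% interval. If an expected precision is to replace the claim of stable estimates, label it illustrative. For 12 dropouts among 60, the Wilson 95% interval is 11.8% to 31.8%, assuming 60 independent participants; correlation within groups could widen it. This costs nothing beyond defining the denominators.
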